- The results of all screening assessments and evaluations must be completed and reviewed by the investigator prior to the Baseline Visit. Informed consent may be obtained up to 4 weeks prior to C1D1.
- Baseline assessments can be performed on Day -1 or on C1D1 prior to treatment.
- Subjects benefiting from study treatment in the opinion of the investigator will continue treatment until disease progression, intolerable toxicity, subject noncompliance with safety or efficacy assessments, initiation of another anticancer therapy, voluntary discontinuation by the subject at any time, or study termination by the sponsor, whichever occurs first.

- e. Subjects will be followed every 3 months for 1 year or until death whichever occurs first, as per the protocol.
- f. A serum or urine pregnancy test will be performed at the Screening and Baseline Visits (or within 72 hours prior to the first dose of study medication) and at the off visit in women of childbearing potential.
- g. A Lansky play score or Karnofsky performance status score will be obtained at the Screening, Baseline, and Cycle 2 Day 1 visits, and every subsequent cycle visit thereafter.
- h. A comprehensive physical examination (including a neurological examination) will be performed at the Screening and Baseline Visits (only if screening physical examination was performed >7 days prior to C1D1), C1D15, Day 1 visit of each subsequent cycle, and at the Off-treatment Visit. A symptom-directed physical examination will be performed on C1D1 and at any time during the study, as clinically indicated.
- i. Assessments will include vital signs (resting BP, HR, RR, and body temperature, and weight. Blood pressure that is consistently above the 95th percentile for sex, age, and height/length requires further evaluation. For blood pressure management, please refer to [Section 9.4.1.3](#) and [Figure 2](#) in the protocol.
- j. Single 12-lead ECG. Subject must be in the recumbent position for a period of 5 minutes prior to the ECG.
- k. An echocardiogram is performed during screening, every 16 weeks, and at end of treatment visit, or sooner if clinically indicated.
- l. Clinical chemistry and hematology results must be reviewed prior to administration of study drug on C1D1 and within 48 hours after dispensing study drug for all subsequent cycles. Scheduled assessments may be performed within 72 hours prior to the visit. If \geq Grade 3 hematologic or clinical chemistry toxicity, repeat laboratory test and AEs assessment at least every 3 days (until improvement to <Grade 3). Guaiac fecal occult blood test (FOBT) should be performed. TSH should be assessed for all subjects, free T4 and thyroglobulin should be assessed only for RR-DTC subjects. See [Table 6](#).
- m. Urine dipstick testing should be performed every on Day 1, 8, 15 and 22 for cycles 1-3, bi-weekly thereafter or more frequently as clinically indicated and at the off-treatment visit. For subjects with history of proteinuria \geq 2+, urine dipstick testing should be performed until the results have been 1+ or negative for 3 consecutive months. If a new event of proteinuria \geq 2+ occurs, the subject must resume the Day 15 urine dipstick testing for evaluation of proteinuria until results are 1+ or negative for 3 consecutive months. Subjects who have \geq 2+ proteinuria on dipstick urinalysis should perform a spot P/C test and if possible undergo a 24-hour urine collection. Urine glucose should be performed as shown in [Table 8](#) as part of urine dipstick. Also see [Table 6](#).
- n. PK blood samples drawn 0.5-4 hours and 6-10 hours postdose on C1D1 and predose, 0.5-4 hours and 6-10 hours postdose on C1D15 and predose and 2-12 hours postdose on C2D1. Study Treatment PK blood samples drawn also on the day of tumor assessment (Predose). If the tumor assessments fall on the same day as study treatment PK samples, they need not be collected again to avoid duplicate samples. If dose interruption is necessary at these time points, only a predose sample should be collected, if possible.
- o. **Screening:** Tumor assessments using CT/MRI of the neck (DTC only), CT chest, abdomen, pelvis, and other areas of known disease or newly suspected disease should be performed within 28 days prior to C1D1. Scans of the abdomen, pelvis, and other areas of the body may be done with MRI instead of CT, but evaluation of the chest should be done with CT. CT scans should be performed with oral and iodinated IV contrast and MRI scans should be performed with IV gadolinium chelate.
- Treatment Phase:** Tumor assessments of the neck (DTC only), chest, and other areas of known disease at Screening or newly suspected disease should be performed every 8 weeks (within week 8) from C1D1 during the Treatment Phase (or sooner if there is evidence of progressive disease) and should use the same methodology (CT or MRI) and scan acquisition techniques (including use or nonuse of IV contrast) as was used for the screening assessments. Tumor response will be assessed according to RECIST 1.1. An initial assessment of CR or PR must be confirmed not less than 4 weeks after achievement of the initial response. After treatment discontinuation, tumor assessment should continue to be performed every 8 weeks until documentation of progression for 1 year or start of a new anticancer agent (refer to [Section 9.5.1.3](#)).
- p. Brain CT with contrast or MRI pre- and post- gadolinium contrast will be performed at the Screening Visit, and as clinically indicated. For subjects with protocol-eligible treated brain metastases, brain CT/MRI will be performed at all tumor assessment time points.
- q. Height will be assessed at the Baseline Visit, Day 1 of every 3 cycles during the Treatment Phase, at the Off-treatment Visit, and every 3 months during the Post-treatment Follow-up. Proximal tibial growth plates x-rays should be conducted at baseline, and at the Off-treatment visit.
 - r. Blood samples will be collected at the Baseline Visit, C1D15, Day 1 of all subsequent cycles, at the Off-treatment Visit for blood serum sample to measure factors implicated in angiogenesis. For subjects ongoing after the data cutoff date for the primary analysis, blood samples will be collected at the Off-Treatment Visit.
- s. An archival tumor sample from the most recent surgery or biopsy for identification of predictive biomarkers and pathology review may be collected at any time during the study, unless no such material is available.
- t. Collection of whole blood to obtain genomic DNA will be performed at the Baseline Visit. If sampling is not performed predose, sampling may occur at any subsequent visit in which other blood sampling is scheduled to occur. Pharmacogenomic markers of drug metabolism and drug transport may be assessed.
- u. Survival data will be collected every 3 months until death or 1 year as per the protocol. All anticancer therapies will be collected.

- v. Concomitant medications will be recorded throughout the study and for 30 days after last dose. All anticancer therapy will be recorded until time of death or termination of Survival Follow-up.
- w. AEs will be recorded from the date of signed informed consent, throughout the study, and for 30 days after last dose. SAEs irrespective of relationship to study treatment must be reported as soon as possible but not later than 24 hours. A diary will be provided to the subject to capture any abnormal gastrointestinal symptoms (e.g., diarrhea, abdominal discomfort, cramps, etc) experienced during the study.

Table 9 Schedule of Assessments – Cohorts 3A and 3B – Osteosarcoma

Phase	Pretreatment		Treatment ^a (All cycles are 21 days in duration)															Post-Treatment			
	Screening ^b	Baseline ^c	Treatment ^d															Off-Tx	Follow-up ^e		
Period	Visit	1	2	3	4	5	6	7	8	9	10	11	12	13	14	15	16	17	99		
Day	-28 to -2	-1	1	8	15	1	8	15	1	8	15	1	8	15	1	8	15	1	8	15	
Procedures/Assessments																					
Informed consent	X																				
Inclusion/exclusion	X	X																			
Demographic data	X																				
Medical/surgical history	X	X																			
Prior medication/ procedures	X	X																			
Pregnancy test ^f	X	X																	X		
Lansky play score/ Karnofsky PS ^g	X	X				X			X			X			X			X			
TNM Staging	X																				
Physical examination ^h	X	X		X		X			X			X			X			X		X	
Vital signs ⁱ	X	X	X	X	X				X			X			X			X		X	
12-lead ECG ^j	X		X			X			X			X			X			X		X	
Echocardiogram ^k	X		Performed every 16 weeks following the first dose of study drug or sooner, if clinically indicated.																		
Clinical chemistry and hematology ^l	X	X		X	X	X				X			X			X			X		X
Guaiac Fecal occult blood test ^l	X	X			X			X			X			X			X			X	
Urine dipstick testing ^m	X	X		X	X	X	X	X	X	X	X	X	X	X	X	X	X	X	X	X	
PK blood samples ⁿ			X			X															
Study treatment			Combination of lenvatinib (QD) + ifosfamide + etoposide (Days 1-3 of Cycles 1-5 only) [based on BSA calculations at Day 1 of each Cycle]																		
Palatability Questionnaire			X																		
Tumor assessments: CT/MRI ^o	X		CT chest and CT/MRI of other areas of known disease at Screening plus any areas of newly suspected disease should be performed every 6 weeks (during Week 6) or sooner if clinically indicated until documentation of disease progression.															X			
Brain CT/MRI ^p	X		Brain scans will be performed at screening and, if clinically indicated during treatment. For subjects																		

Table 9 Schedule of Assessments – Cohorts 3A and 3B – Osteosarcoma

Phase	Pretreatment		Treatment ^a (All cycles are 21 days in duration)															Post-Treatment		
	Screening ^b	Baseline ^c	Treatment ^d														Off-Tx	Follow-up ^e		
Period	Visit	1	2	3	4	5	6	7	8	9	10	11	12	13	14	15	16	17	99	
Visit			Cycle 1			Cycle 2			Cycle 3			Cycle 4			Cycle 5					
Day	-28 to -2	-1	1	8	15	1	8	15	1	8	15	1	8	15	1	8	15			
			with protocol-eligible, treated brain metastases at screening, brain scans should be performed at all tumor assessment time points.																	
Height ^q		X	X												X					X X
Proximal Tibial growth plates x-ray		X																		X
Pharmacodynamic biomarkers ^r		X		X		X			X			X			X					
Archival tumor block or slides ^s										X										
Blood sample for pharmacogenetic/pharmacogenomic analysis ^t		X																		
Survival ^u															X					X
Concomitant medications ^v																				X
AEs/SAEs ^w																				X
Safety Monitoring (call at C1D8)				X																

AE = adverse event, BP = blood pressure, C1D1 = Cycle 1/Day 1, C1D2 = Cycle 1/Day 2, C1D8 = Cycle 1/Day 8, C1D15 = Cycle 1/Day 15, CR = complete response, CT = computerized tomography, ECG = electrocardiogram, h = hour, HR = heart rate, MRI = magnetic resonance imaging, PBMC = peripheral blood mononuclear cells, PK = pharmacokinetics, PR = partial response, PS = performance score, RECIST 1.1 = Response Evaluation Criteria in Solid Tumors, version 1.1, RR = respiratory rate, SAE = serious adverse event, TNM = tumor-node-metastasis, Tx = treatment. All subjects who receive suspension formulation must complete the Palatability Questionnaire according to the Schedule of Assessments. If the subject is unable to complete the questionnaire this must be done by their parents or their legal guardian (Appendix 13).

- a. Efforts should be made to conduct study visits on the day scheduled (± 1 day).
- b. The results of all screening assessments and evaluations must be completed and reviewed by the investigator prior to the Baseline Visit. Informed consent may be obtained up to 4 weeks prior to C1D1.
- c. Baseline assessments can be performed on Day -1 or on C1D1 prior to treatment.
- d. Subjects benefiting from study treatment in the opinion of the investigator will continue treatment until disease progression, intolerable toxicity, subject noncompliance with safety or efficacy assessments, initiation of another anticancer therapy, voluntary discontinuation by the subject at any time, or study termination by the sponsor, whichever occurs first.
- e. Subjects will be followed every 3 months for 1 year or until death as per the protocol.
- f. A serum or urine pregnancy test will be performed at the Screening and Baseline Visits (or within 72 hours prior to the first dose of study medication) and at the Off-treatment Visit in women of childbearing potential.
- g. A Lansky play score or Karnofsky performance status score will be obtained at the Screening, Baseline, and Cycle 2 Day 1 Visits, and Day 1 of every subsequent cycle visit thereafter.
- h. A comprehensive physical examination (including a neurological examination) will be performed at the Screening and Baseline Visits (only if screening physical examination was performed >7 days prior to C1D1), C1D8, and Day 1 visit of each subsequent cycle, and at the Off-treatment Visit. A symptom-directed physical examination will be performed on C1D1 and at any time during the study, as clinically indicated.
- i. Assessments will include vital signs (resting BP, HR, RR, and body temperature), and weight. Blood pressure that is consistently above the 95th percentile for sex, age, and height/length requires further evaluation. For blood pressure management, please refer to [Section 9.4.1.3](#) and [Figure 2](#) in the protocol.
- j. Single 12-lead ECG. Subjects must be in the recumbent position for a period of 5 minutes prior to the ECG.
- k. An echocardiogram is performed during screening, every 16 weeks, and at end of treatment visit, or sooner if clinically indicated.
- l. Clinical chemistry and hematology results must be reviewed prior to administration of study drug on C1D1 and within 48 hours after dispensing study drug for all subsequent cycles. Scheduled assessments may be performed within 72 hours prior to the visit. If \geq Grade 3 hematologic or clinical chemistry toxicity, repeat laboratory test and AEs assessment at least every 3 days (until improvement to $<$ Grade 3). Guaiac fecal occult blood test (FOBT) should be performed. TSH should be assessed for all subjects, See [Table 6](#).
- m. Urine dipstick testing should be performed on Day 1 or more frequently as clinically indicated for 4 cycles, biweekly thereafter, and at the Off-treatment Visit. For subjects with a history of proteinuria $\geq 2+$, urine dipstick testing should be performed until the results have been 1+ or negative for 3 consecutive months. If a new event of proteinuria $\geq 2+$ occurs, the subject must resume the Day 15 urine dipstick testing for evaluation of proteinuria until results are 1+ or negative for 3 consecutive months. Subjects who have $\geq 2+$ proteinuria on dipstick urinalysis should perform a spot P/C test and if possible undergo a 24-hour urine collection. Urine glucose should be performed as shown in [Table 9](#) as part of the urine dipstick. Also, see [Table 6](#).
- n. Study Treatment PK blood samples drawn 0.5-4 hours and 6-10 hours postdose on C1D1, and predose and 2-12 hours postdose on C2D1. Study Treatment PK blood samples drawn also on the day of tumor assessment (predose). If the tumor assessments fall on the same day as study treatment PK samples, they need not be collected again to avoid duplicate samples. If dose interruption is necessary at these time points, only a predose sample should be collected, if possible.
- o. **Screening:** Tumor assessments of the chest, abdomen, pelvis, and other areas of known disease or newly suspected disease should be performed within 28 days prior to C1D1. Scans of the abdomen, pelvis, and other areas of the body may be done with MRI instead of CT, but evaluation of the chest should be done with CT. CT scans should be performed with oral and iodinated IV contrast and MRI scans should be performed with IV gadolinium chelate
Treatment Phase: Tumor assessments of the chest, and other areas of known disease at Screening or newly suspected disease should be performed every 6 weeks (within Week 6) from C1D1 during the Treatment Phase (or sooner if there is evidence of progressive disease) and should utilize the same methodology (CT or MRI) and scan acquisition techniques (including use or nonuse of IV contrast) as was used for the screening assessments. Tumor response will be assessed according to RECIST 1.1. Subjects who discontinue must complete the off-treatment tumor assessment. Any CR or PR must be confirmed not less than 4 weeks following the initial achievement of the response. After treatment discontinuation, tumor assessment should continue to be performed every 6 weeks until documentation of progression for 1 year or start of a new anticancer agent (refer to [Section 9.5.1.3](#)).
- p. Brain CT with contrast or MRI pre- and post- gadolinium contrast will be performed at the Screening Visit, and as clinically indicated. For subjects with protocol-eligible treated brain metastases, brain CT/MRI will be performed at all tumor assessment time points.

- q. Height will be assessed at the Baseline Visit, Day 1 of every 3 cycles during the Treatment Phase, at the Off-treatment Visit and every 3 months during the Post-treatment Follow-up for 1 year. Proximal tibial growth plates x-rays should be conducted at baseline and at the Off-treatment Visit. Hand and wrist x-rays and tibial growth plate x-rays will be optional for Germany.
- r. Blood samples will be collected at the Baseline Visit, C1D8, Day 1 of all subsequent cycles, and at the Off-Treatment assessment for blood serum sample to measure factors implicated in angiogenesis. For subjects ongoing after the data cutoff data for the primary analysis, blood samples will be collected at the Off-Treatment Visit.
- s. An archival tumor sample from the most recent surgery or biopsy for identification of predictive biomarkers and pathology review may be collected at any time during the study, unless no such material is available.
- t. Collection of whole blood to obtain genomic DNA will be performed at the Baseline Visit. If sampling is not performed predose, sampling may occur at any subsequent visit in which other blood sampling is scheduled to occur. Pharmacogenetic markers of drug metabolism and drug transport may be assessed.
- u. Survival data will be collected every 3 months until death or 1 year as per the protocol. All anticancer therapies will be collected.
- v. Concomitant medications will be recorded throughout the study and for 30 days after last dose. All anticancer therapy will be recorded until time of death or termination of Survival Follow-up.
- w. AEs will be recorded from the date of signed informed consent, throughout the study, and for 30 days after last dose. SAEs irrespective of relationship to study treatment must be reported as soon as possible but not later than 24 hours. A diary will be provided to the subject to capture any abnormal gastrointestinal symptoms (eg, diarrhea, abdominal discomfort, cramps) experienced during the study.

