Clinical laboratory tests to be performed, including hematology, chemistry, and urinalysis, are summarized in Table 6. Subjects should be in a seated or supine position during blood collection. The Schedule of Assessments ([Table 7](#), [Table 8](#), and [Table 9](#)) shows the visits and time points at which blood for clinical laboratory tests and urine for urinalysis will be collected in the study.

Table 6 Clinical Laboratory Tests

Category	Parameters
Hematology	Hematocrit, hemoglobin, platelets, RBC count, and WBC count with differential (bands, basophils, eosinophils, lymphocytes, monocytes, neutrophils), MCH, MCHC, MCV
Chemistry	
Electrolytes	Bicarbonate, chloride, potassium, sodium
Liver function tests	ALT, alkaline phosphatase, aspartate AST, conjugated (direct) bilirubin ^a , total bilirubin
Renal function tests	BUN or urea, creatinine
Other chemistries	Albumin, amylase, calcium, glucose, LDH, lipase, magnesium, phosphorus, total protein, uric acid, Guaiac fecal occult blood test (FOBT)
Urinalysis for microscopy ^b	RBCs/high-power-field (HPF)
Urine dipstick testing ^{b,c}	Blood, protein, glucose
Other	Pregnancy test (serum or urine β -hCG), TSH, free T4 levels, thyroglobulin ^d

ALT = alanine aminotransferase; AST = aspartate aminotransferase; BUN = blood urea nitrogen; β hCG = beta-human chorionic gonadotropin; LDH = lactate dehydrogenase; MCH = mean corpuscular hemoglobin; MCHC = mean corpuscular hemoglobin concentration; MCV = mean corpuscular volume; RBC = red blood cells; T4 = thyroxine; TSH = thyroid stimulating hormone; WBC = white blood cells.

a: Direct bilirubin should be assessed if total bilirubin is elevated.

b: If urine dipstick testing suggests a urinary tract infection, or if clinically indicated, a urine microscopy, culture, and sensitivity should be performed at the institution's laboratory

c: If urine protein is $\geq 2+$, then a spot test for protein-creatinine ratio and if possible, a 24-hour urine collection should be done to quantify the 24 hour urine protein excretion.

d: For DTC subjects, TSH, free T4, and thyroglobulin should be tested. TSH should be assessed for all subjects.

All clinical laboratory tests during the study will be performed by local laboratories. All hematology, blood chemistry (including pregnancy test, as applicable), and urinalysis

samples are to be obtained prior to study drug administration and sent to the local laboratory on the day of collection unless otherwise instructed.

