A serum β -hCG test will be performed for females of childbearing potential (see definition included in the Inclusion/Exclusion criteria, [Sections 9.3.1](#) and [9.3.2](#)). A serum or urine pregnancy test will be performed at Screening and Baseline (or within 72 hours prior to the first dose of study medication) and at the Off-treatment Visit in women of childbearing potential. Blood and urine samples will be taken at designated time points as specified in the Schedule of Assessments [Table 7](#), [Table 8](#), and [Table 9](#)).

Echocardiogram

An echocardiogram to assess left ventricular ejection fraction (LVEF) will be performed during the screening phase, every 16 weeks following the first dose of study drug while the subject is on treatment or sooner, if clinically indicated, and at (or within 1 week following) the off-treatment assessment. LVEFs as assessed by the institution will be entered onto the CRF. Investigator assessment will be based upon institutional reports.

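### Table 9 footnote m (Cohorts 3A/3B) opens with a Day-1-only urine dipstick minimum that conflicts with the weekly row it annotates: a minor wording correction

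*Protocol*

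**What the plan says.** Protocol Section 9.5.2.1, Table 9 (Cohorts 3A and 3B), has a row headed "Urine dipstick testing". It is marked at Screening and Baseline, blank at Cycle 1 Day 1 (C1D1), and marked at C1D8, C1D15 and Days 1, 8 and 15 of later cycles. Baseline may be done on Day -1 or before dosing on C1D1, so the blank loses nothing.

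Footnote m on that row begins: "Urine dipstick testing should be performed on Day 1 or more frequently as clinically indicated for 4 cycles, biweekly thereafter". It then adds the off-treatment visit.

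Two later sentences of the same footnote point towards the row. Glucose comes first: "Urine glucose should be performed as shown in" Table 9, as part of the dipstick. Table 6 (Section 9.5.1.5) gives the content of that one dipstick as "Blood, protein, glucose". The other sentence says that after a new result of 2+ or more, "the subject must resume the Day 15 urine dipstick testing for evaluation of proteinuria".

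Section 9.4.1.6 sends sites to the schedule tables for the frequency of proteinuria assessment. Section 9.5.1.5, Laboratory Measurements, says the Schedule of Assessments "shows the visits and time points at which blood for clinical laboratory tests and urine for urinalysis will be" collected.

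The matching footnotes for the single-agent cohorts (Tables 7 and 8) list Days 1, 8, 15 and 22 for Cycles 1 to 3.

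**The concern.** A Day 1 minimum and a weekly minimum cannot both be the rule, and the sentence gives the lighter schedule. Taken alone it also tests every 21 days in Cycles 1 to 4 and then every 14 days (reading biweekly as every two weeks). Monitoring would be sparsest while toxicity is first being characterised. That looks like a drafting slip rather than a choice.

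Proteinuria matters for this drug. Section 7.1.3.2 names hypertension and proteinuria as the most common DLTs. Section 9.4.1.1 makes Grade 3 proteinuria a DLT, with a Cohort 3A window of Day 1 to Day 21. Under Section 9.4.1.6, a dipstick of 2+ or more triggers the spot protein-creatinine ratio used for grading. The grade then drives the interruptions and reductions in Table 3 (Section 9.4.1.2). The two-weekly dipsticks in Section 9.4.1.6 apply only after a 2+ result, so they do not help find the first one. A symptom-free case that is not dipped may not enter this pathway until the next scheduled test.

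**Working it through.** Inputs:
- Cycle length in Table 9 is 21 days, so nominal study day = (cycle − 1) × 21 + cycle day.
- The Cohort 3A DLT window is Day 1 to Day 21 (Section 9.4.1.1).
- Laboratory and urinalysis "samples are to be obtained prior to study drug administration" (Section 9.5.1.5). A C1D1 test is therefore not post-dose, and the days that count are 2 to 21.
- Visits may move by ±1 day (Table 9 footnote a).
- Scheduled assessments may be done up to 72 hours before the visit (Section 9.5.1.5, Laboratory Measurements, and Table 9 footnote l). This sits beside the chemistry and hematology rules, so whether it covers dipsticks is arguable.

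Reading the row. Because the table is extracted text, the column alignment was checked against two rows whose footnotes state their days: physical examination (C1D8, then Day 1 of later cycles) and PK (C1D1 and C2D1). Both line up. The protocol prints no count of dipsticks; the marks give two in the window, C1D8 and C1D15.

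Nominal post-dose test days through Cycle 4 (Day 84):

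| Schedule | Days | In Days 2–21 | By Day 84 |
|---|---|---|---|
| Row | 8, 15, 22, 29, 36, 43, 50, 57, 64, 71, 78 | 2 | 11 |
| First sentence alone | 22, 43, 64 | 0 | 3 |

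Difference by Day 84: 11 − 3 = 8 tests (Days 8, 15, 29, 36, 50, 57, 71, 78).

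If C2D1 testing is brought forward, it falls on Day 22 − 1 = 21 under the visit window, or Day 22 − 3 = 19 under the 72-hour allowance. Either way the count on Days 2 to 21 becomes 1 for the sentence and 3 for the row.

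Maximum added detection delay (proteinuria the row would find at C1D8 but the sentence only at C2D1):
- Nominal: 22 − 8 = 14 days.
- With ±1 day: smallest (22 − 1) − (8 + 1) = 12; largest (22 + 1) − (8 − 1) = 16.
- With the 72-hour allowance as well: smallest (22 − 1 − 3) − (8 + 1) = 9; largest (22 + 1) − (8 − 1 − 3) = 19.

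If the row is followed, the result is 2 tests in the window, 11 by Day 84 and no added delay. These are schedule counts; no distribution of onset times is assumed.

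**The case against.** The strongest reply is that the protocol largely answers the question itself. Glucose is to follow the Table 9 row as part of the dipstick, and Table 6 puts protein on the same strip. Doing glucose as marked therefore means testing protein on C1D8 and C1D15. Section 9.4.1.6, which governs proteinuria, defers to the schedule. The sentence sets a floor and forbids nothing the row marks. This stands: the row is the better-supported reading, and a count of 0 requires a site to act on one sentence and ignore the rest.

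It does not remove the conflict. The footnote is itself part of the schedule those sections point to, and no text says the row prevails. Two of the supporting texts are also weaker than they look. The Day 15 sentence covers only new results of 2+ or more and may mean the extra monitoring in Section 9.4.1.6. In Section 9.5.1.5, "Blood and urine samples will be taken at designated time points as specified in the" Schedule of Assessments appears in the pregnancy-test paragraph.

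A second reply is that chemistry and vital signs are marked at C1D8 and C1D15 and could prompt a clinically indicated dipstick. They could, but they do not replace it.

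A third is that the main consequence is spent, because SAP Section 3.4.2 reports the Cohort 3A recommended dose as already determined. That also stands and lowers the weight of the point.

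A reader might go further and infer that proteinuria DLTs were missed in Cohort 3A, or that the recommended dose of lenvatinib 14 mg/m² with ifosfamide and etoposide is unsafe or needs re-deriving. The documents do not support this. They do not show which reading sites used, and they report no missed DLT.

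**Conclusion.** The contradiction is real, and the sentence is wrong as written, but it is minor. It is a wording inconsistency rather than a design choice, since the row shows weekly testing in the marked cycles. Its size is conditional on a site acting on the first sentence alone. In that case there are 0 rather than 2 nominal post-dose dipsticks on Days 2 to 21 (1 if C2D1 testing is brought forward), and up to 14 days of added detection delay. That delay is 12 to 16 days with ±1 day visits, or 9 to 19 if the 72-hour allowance also covers dipsticks. At a site following the row there is no effect. What remains at stake is consistent proteinuria monitoring and timely dose management for subjects treated under Table 9, including Cohort 3B.

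**What to change.** Amend the first sentence of Table 9 footnote m to read, in substance:

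*Test urine by dipstick on Days 8 and 15 of Cycle 1 and on Days 1, 8 and 15 of later cycles as marked in Table 9; biweekly in cycles beyond the marked columns; more often as clinically indicated; and at the Off-treatment Visit.*

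The last three clauses must stay. Lenvatinib may continue past the marked cycles, and a sentence that only copied the row would leave no routine frequency there and would drop the off-treatment test.

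The cost is one sentence in an amendment. Sites already following the row gain no tests in the marked cycles. Sites that acted on the old sentence would add up to 8 dipsticks per subject over Cycles 1 to 4, plus any extra weekly tests marked in later cycles, where the sentence now asks for biweekly testing. All fall on visit days Table 9 already lists, and C1D8 and C1D15 are also marked for chemistry.

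No SAP change is needed. The by-subject urinalysis listing in SAP Section 5.6.3.3 can already show any Cohort 3A subject with no dipstick on Days 2 to 21.
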